1.0 Objectives

1.1 Describe the purpose, specific aims, or objectives of this research.

Response:

The purpose of this study is to compare the anxiety and pain levels of patients when using Buzzy with ice wings, Vapocoolant, and placebo during venipuncture procedure in pediatric patients.

1.2 State the hypotheses to be tested, if applicable.

NOTE: A hypothesis is a specific, testable prediction about what you expect to happen in your study that corresponds with your above listed objectives.

Response:

We hypothesize that the Buzzy will provide greater pain relief based on patient self-report and parent report of their child's pain as well as independent observation when compared to Vapocoolant or placebo.

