The Procedure Behavior Checklist (PBCL) is a well-established observational pain measure that has been validated for children 3-18 years old. It evaluates both the intensity and frequency of 10 defined behaviors that indicate distress. The PBCL was developed by Katz et al in 1980. On a scale of 1-5, it rates child's muscle tension, screaming, crying, restraint needed, verbalized pain, anxiety, etc. The scores are then added together to give a final score. The Faces Pain Scale – Revised (FPS- R; Hicks et al 1990) is a self-report measure used to assess the intensity of children's pain. It consists of 6 faces, with each one representing an increasing degree of pain moving from left to right in increments of two starting from zero (0, 2, 4, 6, ,8, 10).

Both of the PBCL and Faces pain scale –revised have been validated tool and used frequently in clinical practices and studies when evaluate patient's pain scale.

In this study, we will compare the effectiveness of pain release devices i.e. buzzy, with vapocoolants or placebo. We will use the validated PBCL and Faces pain scale-revised methods as the pain evaluation tools. To our knowledge, no study has been performed on comparison of the effectiveness of these commonly used pain release devices. We hope to contribute some useful information in this field through our research.

3.2 *Include complete citations or references.*

Response:

*Blount R. L., Zempsky W. T., Jaaniste T., Evans S., Cohen L. L., Devine K. A., Zeltzer L. K. Management of pain and distress due to medical procedures. In: Roberts M C, Steele R, editors. *Handbook of pediatric psychology*. 4th Ed. New York: Guilford Press; 2009. pp.171–188.*

Cohen Reis E. & Holubkov R. (1997). Vapocoolant spray is equally effective as EMLA cream in reducing immunization pain in school-aged children. Pediatrics, 100 (6).

Hamilton J.G. (1995). Needle phobia: A neglected diagnosis. Journal of Family Practice, 41 (2):169-175.

Hicks C.L., von Baeyer, C.L., Spafford P.A., van Korlaar I. & Goodenough B. The Faces Pain Scale - Revised: toward a common metric in pediatric pain measurement. Pain 93(2001) 173-183.

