17.0 Data Management and Analysis

17.1 *Describe the data analysis plan, including any statistical procedures. This section applies to both quantitative and qualitative analysis.*

Response:

All data analyses will be performed with SAS (version 9.2; SAS Institute, Inc., Cary, NC) and R (version 3.0.3) software. Chi-square and Fisher's exact test will be used to compare adverse events (e.g., systemic reaction, anaphylaxis, SOB, dyspnea, excess bleeding or hematoma formation), venipuncture and catheterization first attempt success, and number of patients with no to mild pain during needle insertion.

The Kruskal-Wallis test will be used to compare each of the two observers' assigned scores on the PBCL across three time periods: pre, procedure and post-procedure. Pre-procedure is defined as the time period prior to needle insertion including the placement of Vapocoolant, pain control or sham device up to needle insertion. The procedure period is defined as needle insertion through withdrawal. Post-procedure is defined as the 2 minute time period after needle withdrawal. Only patient and observer pain scores will be used for first-time needle insertion. If first attempt is failed, subject will be withdrawn from the study. Comparisons of pain scores of the five intervention groups to placebo (sham device) will be analyzed via ANOVA.

17.2 If applicable, provide a power analysis.

NOTE: This may not apply to certain types of studies, including chart/records reviews, survey studies, or observational studies. This question is asked to elicit whether the investigator has an adequate sample size to achieve the study objectives and justify a conclusion.

Response:

For chi-square analysis, based on a medium effect size of 0.3, alpha of 0.05, degree of freedom of 8, and 80% power it is estimated we will need a total of 168 subjects (56 per group). (*QFAB Bioinformatics*. 2015)

17.3 Describe any procedures that will be used for quality control of collected data.

Response:

Our RA will double check the data form to assure accuracy and completeness of data collection, if there is any missed data point, the RA will fill in the missing information immediately.

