32.0 Humanitarian Use Devices

N/A: This study does not involve humanitarian use devices. This does not apply.

32.1 For Humanitarian Use Device (HUD) uses provide a description of the device, a summary of how you propose to use the device, including a description of any screening procedures, the HUD procedure, and any patient follow-up visits, tests or procedures.

Response:

32.2 For HUD uses provide a description of how the patient will be informed of the potential risks and benefits of the HUD and any procedures associated with its use.

Response:

Data Management and Analysis

All data analyses will be performed with SAS (version 9.2; SAS Institute, Inc., Cary, NC) and R (version 3.0.3) software. Chi-square and Fisher's exact test will be used to compare adverse events (e.g., systemic reaction, anaphylaxis, SOB, dyspnea, excess bleeding or hematoma formation), venipuncture and catheterization first attempt success, and number of patients with no to mild pain during needle insertion.

The Kruskal-Wallis test will be used to compare each of the two observers' assigned scores on the PBCL across three time periods: pre, procedure and post-procedure. Pre-procedure is defined as the time period prior to needle insertion including the placement of Vapocoolant, pain control or sham device up to needle insertion. The procedure period is defined as needle insertion through withdrawal. Post-procedure is defined as the 2 minute time period after needle withdrawal. Only patient and observer pain scores will be used for first-time needle insertion. If first attempt is failed, subject will be withdrawn from the study. Comparisons of pain scores of the five intervention groups to placebo (sham device) will be analyzed via ANOVA.

For chi-square analysis, based on a medium effect size of 0.3, alpha of 0.05, degree of freedom of 8, and 80% power it is estimated we will need a total of 168 subjects (56 per group). (QFAB Bioinformatics. 2015)

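### The only power statement is for a chi-square test with 8 df, which no described analysis of this three-arm trial has; the score analyses have no power statement

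*Combined protocol and SAP*

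**What the plan says.** Section 17.2 gives the trial's only power statement: "For chi-square analysis, based on a medium effect size of 0.3, alpha of 0.05, degree of freedom of 8, and 80% power". The same text closes the document, in the Data Management and Analysis paragraphs after section 32.0: "degree of freedom of 8, and 80% power it is estimated we will need a total of 168 subjects (56 per group").

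Section 17.1 assigns the tests:

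- Chi-square or Fisher's exact test: adverse events, first-attempt success, and "number of patients with no to mild pain during needle insertion".
- Kruskal-Wallis: "The Kruskal-Wallis test will be used to compare each of the two observers' assigned scores on the PBCL". The comparison is described across the pre-procedure, procedure and post-procedure periods, not between arms.
- ANOVA: "Comparisons of pain scores of the five intervention groups to placebo (sham device) will be analyzed via ANOVA".

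Sections 5.1 and 10.1 describe three arms (Buzzy, vapocoolant, sham) of 56 each. Section 2.1 makes the primary outcome a greater reduction in anxiety and pain with Buzzy than with either comparator. Section 1.2 judges pain relief "based on patient self-report and parent report of their child's pain as well as independent observation". No section picks one score or time point as primary.

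**The concern.** A power statement should describe the test that will answer the main question. This one is for a test with 8 df, and 8 df does not follow from three arms and the yes/no outcomes listed for chi-square. The scores that measure pain and distress go to other tests, for which the plan gives no effect size, SD or power.

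At stake is how the result will be read. If Buzzy does not separate from vapocoolant or sham, a reader may set that null result against an 80% figure that never applied to the comparison. The prompt at 17.2 asks whether the sample is adequate for the study objectives, and the present answer does not address them.

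**Working it through.** **Inputs from the documents.** w = 0.3, alpha = 0.05, 8 df, 80% power, N = 168 (17.2); three arms of 56 (5.1, 10.1). No mean difference or SD is given for any score, so every f and d below is either a detectable value or an assumption.

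**1. The plan's own figure.** Chi-square power is the probability that a noncentral chi-square with noncentrality λ = N·w² exceeds the 5% critical value. For 8 df and 80% power, λ = 15.022, so N = 15.022 / 0.09 = 166.9. That is 167, or 168 in three equal arms. Power at 168 is 80.3%. The figure reproduces.

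**2. Which table has 8 df?** For r groups by c categories, df = (r − 1)(c − 1).

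| Table | df | N for 80%, w = 0.3 | Power at 168, w = 0.3 |
|---|---|---|---|
| 3 arms × yes/no (outcomes listed in 17.1) | 2 | 9.635 / 0.09 = 107.1, so 108 | 94.6% |
| 3 arms × 5 categories | 8 | 166.9, so 167 | 80.3% |
| 5 groups × 3 levels | 8 | 166.9, so 167 | 80.3% |
| 3 arms × 6 FPS-R faces | 10 | 16.241 / 0.09 = 180.5, so 181 | 76.4% |

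Neither 8-df table is planned:

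- A single PBCL item rated 1 to 5 would supply five categories, but section 3.1 says of the items: "The scores are then added together to give a final score".
- Adverse-event types could be counted as five, but 17.1 offers them only as examples and plans no such cross-table.
- Five groups by three levels would fit the mention of five intervention groups in 17.1, but this trial has three arms.
- The FPS-R does not help: "It consists of 6 faces, with each one representing an increasing degree of pain", which gives 10 df.

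At N = 168 the 2-df test has 80% power at w = √(9.635 / 168) = 0.239.

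**3. What 168 offers for the score analyses**, with 56 analysed per arm.

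- Three-arm ANOVA (noncentral F with 2 and 165 df, λ = N·f²): 80% power at f = 0.242; 82.8% at an assumed f = 0.25.
- One Buzzy contrast with the pooled ANOVA error (165 df, noncentrality d·√(56/2)): 80% power at d = 0.533 (two-sided 0.05) or 0.587 (two-sided 0.025, if two contrasts share 0.05). At an assumed d = 0.5, power is 74.9% or 65.0%.
- Kruskal-Wallis, if it were restated as a between-arm test: multiply N by an asymptotic relative efficiency of 0.955 (normal data) or 0.864 (lower bound), so 168 becomes 160.4 or 145.2. At an assumed f = 0.25, power is then about 81% or 76%.

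**4. Enrolled or analysed.** Section 5.1 enrols 168. Sections 20.1 and 20.2 withdraw a child whose first stick fails and collect no data from that child. No failure rate is given. As an illustration only, 50 analysed per arm (150 in all, about 10% lost) gives 80% power at f = 0.256, and at d = 0.56 (two-sided 0.05) or 0.62 (two-sided 0.025).

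**The case against.** The best defence has three parts. First, the calculation is correct for its inputs, and chi-square tests are planned, one of them on a pain endpoint. Second, 8 df is not absurd, because two kinds of table could produce it. Third, 168 would serve a three-arm ANOVA about as well as the stated 80% suggests: 82.8% at the conventional f = 0.25.

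The first part stands, but the pain endpoint tested by chi-square is yes/no and has 2 df. The second explains how the 8 may have arisen without tying it to a planned analysis. The third is arithmetic on a benchmark the documents do not contain, and it covers the overall three-arm test rather than the Buzzy contrasts that the hypothesis concerns.

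Two stronger readings are tempting and are not supported. One is that the trial is underpowered. The documents give no difference or SD for any score, so this cannot be shown. For the listed 2-df tests the stated 80% is too low rather than too high, although that also depends on w = 0.3, which the plan ties to no endpoint. The other is that ANOVA and Kruskal-Wallis are the primary analyses. That is an inference from sections 1.2, 2.1 and 17.1: no primary test is named, and Kruskal-Wallis as written compares time periods, not arms.

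Nor do the documents show that fewer than 56 per arm will be analysed. They leave it unclear, and the loss figure above is an assumption.

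**Conclusion.** The point holds and should be fixed. The 168 is correct for w = 0.3 and 8 df, but no analysis described for this three-arm trial has 8 df, and the score analyses have no power statement. The stated 80% is therefore not the power of any described analysis. How far it is off depends on the test chosen: at N = 168 it could be 94.6% (2-df chi-square, w = 0.3), 82.8% (ANOVA, assumed f = 0.25), or 75% or 65% (one Buzzy contrast, assumed d = 0.5, two-sided 0.05 or 0.025).

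These figures assume equal arms with 56 analysed in each; f = 0.25, d = 0.5 and the alpha of 0.025 are not from the documents. The finding concerns the justification of 168, not whether 168 is enough.

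**What to change.** 1. In 17.1, name the primary score, its time point and the between-arm test. Correct the mention of five intervention groups to the three-arm design. State the Buzzy-versus-vapocoolant and Buzzy-versus-placebo contrasts and the alpha for each.

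2. Replace the 8-df sentence in 17.2, and its repeat after section 32.0, with power for the named test at 56 analysed per arm:
   - Three-arm ANOVA: 80% power at f = 0.242. Each Buzzy contrast has 80% power at d = 0.53 (two-sided 0.05) or d = 0.59 (two-sided 0.025), and 75% or 65% at an assumed d = 0.5.
   - PBCL: first restate Kruskal-Wallis as a between-arm comparison, then give its own figure (about 76 to 81% at an assumed f = 0.25).
   - The yes/no outcome of no to mild pain: 2 df, 94.6% at w = 0.3, and 80% at w = 0.24.

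   Add the difference judged worth detecting, with its source, because a detectable effect describes 168 but does not justify it. Label f, d and any SD or correlation as assumptions. If a before-after change is analysed, any conversion to single-time SDs must state that it assumes equal pre and post SDs.

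3. Say in one line whether 168 is the number enrolled (5.1) or the number analysed after withdrawals (20.1, 20.2). If enrolled, add detectable effects at an assumed loss, labelled illustrative, such as the 50-per-arm figures above. If analysed, 5.1 must allow more than 168 to be randomised.

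The restatement is wording only and needs no extra patients. The sponsor must choose the primary score, the time point, the test and the alpha per contrast. The downside is that the stated power becomes less favourable for the pairwise contrasts.

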18.0 Confidentiality

A. Confidentiality of Study Data

Describe the local procedures for maintenance of confidentiality of study data and any records that will be reviewed for data collection.

18.1 A. Where and how will all data and records be stored? Include information about: password protection, encryption, physical controls, authorization of access, and

*separation of identifiers and data, as applicable. Include physical (e.g. paper) **and** electronic files.*

Response:

Completed paper data form with subject identifier and signed consent/assent documents will be placed in a locked study box in the ED. The study coordinator will collect these documents on a daily basis. The documents will be stored in a locked file cabinet in a research storage room (Conventus, Room 5201, [name]). Each subject's data form will be labeled with a unique study identify number (ID). In addition, we will use a "**subject enrollment log**" to track subject's enrollment and data entry status. This log is attached with this submission. Subject's ID, medical record number, enrollment date, and data entry date will be entered in this log. This log will be stored in a locked file cabinet in the study coordinators' office Room 5201 in the Conventus building.

The data will be entered in a Microsoft excel spread sheet (**Database**) by a trained research assistant. Database will be saved in a password protected UPA secure online drive. No subject's name, DOB, medical record number or Fin Number will be entered in the database. The study ID number will be served as the code key to link the Database and the Subject enrollment log. We need to collect subject's medical record number for the purpose of answering query.

The study coordinator will transfer the subject's video from the camera to a password protected secure UPA online folder, which will also be shared with the two physicians who will reviewed these videos. Then the coordinator will erase the video from the camera.

The two trained physician observers will review the video saved on the password protected secure online folder at their Conventus offices and give a PSCL score for each subject. Video will be erased upon completing the study.

18.2 A. How long will the data be stored?

Response:

Videotapes will be erased upon the end of the study. Paper data form and subject enrollment log will be stored for three years after IRB closes this study. Electronic data base will be stored indefinitely.

18.3 A. Who will have access to the data?

Response:

The PI, study coordinator and research assistant that perform data entry will have access to the data. The two observers will access the video image data.

18.4 A. Who is responsible for receipt or transmission of the data?

Response:

The study coordinator will be responsible for transmitting the data.

18.5 A. How will the data be transported?

Response:

Everything will be transported manually.

B. Confidentiality of Study Specimens

Describe the local procedures for maintenance of confidentiality of study specimens.

N/A: No specimens will be collected or analyzed in this research.
(Skip to Section 19.0)

18.6 B. Where and how will all specimens be stored? Include information about: physical controls, authorization of access, and labeling of specimens, as applicable.

Response:

18.7 B. How long will the specimens be stored?

Response:

18.8 B. Who will have access to the specimens?

Response:

18.9 B. Who is responsible for receipt or transmission of the specimens?

Response:

18.10 B. How will the specimens be transported?

Response:

19.0 Provisions to Monitor the Data to Ensure the Safety of Subjects

N/A: This study is not enrolling subjects, or is limited to records review procedures only. This section does not apply.

NOTE: Minimal risk studies may be required to monitor subject safety if the research procedures include procedures that present unique risks to subjects that require monitoring. Some examples include: exercising to exertion, or instruments that elicit suicidality or substance abuse behavior. In such cases, N/A is not an acceptable response.

19.1 Describe the plan to periodically evaluate the data collected regarding both harms and benefits to determine whether subjects remain safe.

Response:

This is an observational study, involves minimum risk to participant. We do not anticipate any safety issue that may be related with the participation of this study.

19.2 Describe what data are reviewed, including safety data, untoward events, and efficacy data.

Response:

Not applicable.

19.3 Describe any safety endpoints.

Response:

Not applicable.

19.4 Describe how the safety information will be collected (e.g., with case report forms, at study visits, by telephone calls with participants).

Response:

Not applicable.

19.5 Describe the frequency of safety data collection.

Response:

Not applicable

19.6 Describe who will review the safety data.

Response:

Not applicable

19.7 Describe the frequency or periodicity of review of cumulative safety data.

Response:

Not applicable

19.8 Describe the statistical tests for analyzing the safety data to determine whether harm is occurring.

Response:

Not applicable

19.9 Describe any conditions that trigger an immediate suspension of the research.

Response:

Not applicable

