4.0 Study Design

4.1 Describe and explain the study design (e.g. case-control, cross-sectional, ethnographic, experimental, interventional, longitudinal, observational).

Response:

This is a single-center, randomized, open label, placebo controlled clinical trial.

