Two physicians will review the video tape independently, and give a score using the PBCL tool. These two physicians are blinded to the study aims. They will be trained on how to use the PBCL by the PI.

In the event when there is a discrepancy of the PBCL score between the two reviewers, the mean of the two scores will be used as the final score.

10.2 Describe what data will be collected.

NOTE: For studies with multiple data collection points or long-term follow up, consider the addition of a schedule or table in your response.

Response:

We will collect demographic data, reason for venipuncture, PBCL score, facial pain score etc.

10.3 List any instruments or measurement tools used to collect data (e.g. questionnaire, interview guide, validated instrument, data collection form).

Include copies of these documents with your submission.

Response:

The following documents will be used for data collection:

1. Data collection form

2. Procedure behavior check list (PBCL)
3. The Faces Pain scale-revised document.

These documents will be submitted with this IRB application.

10.4 Describe any source records that will be used to collect data about subjects (e.g. school records, electronic medical records).

Response:

Kaleida health Electronic power chart records will be used for data collection.

*10.5 Indicate whether or not **individual** subject results, such as results of investigational diagnostic tests, genetic tests, or incidental findings will be shared with subjects or others (e.g., the subject's primary care physician) and if so, describe how these will be shared.*

Response:

No individual subject results will be shared with the subject or others.

*10.6 Indicate whether or not **study** results will be shared with subjects or others, and if so, describe how these will be shared.*

Response:

Study results will not be shared with subjects or others. The final results of this study may be presented at a conference or published in a peer reviewed journal; however, only group data will be publicized in these circumstances, no individual identifiable information will be released.

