20.0 Withdrawal of Subjects

N/A: This study is not enrolling subjects. This section does not apply.

*20.1 Describe **anticipated** circumstances under which subjects may be withdrawn from the research without their consent.*

Response:

If the first venipuncture procedure is failed, subject will be withdrawn from the study.

20.2 Describe any procedures for orderly termination.

NOTE: Examples may include return of study drug, exit interview with clinician. Include whether additional follow up is recommended for safety reasons for physical or emotional health.

Response:

If a subject is withdrawn from the study, we will not collect any data from the subject.

20.3 Describe procedures that will be followed when subjects withdraw from the research, including retention of already collected data, and partial withdrawal from procedures with continued data collection, as applicable.

Response:

If a subject withdraws from the research in the ED, no study data will be collected for the study. The signed consent/assent document will be kept in the file cabinet in the research office, Conventus building, Room 5201.

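### Adverse events are to be compared by arm, but 19.3 and 19.4 provide no safety endpoint or collection, and 20.1 and 20.2 drop every child whose first stick fails

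*Combined protocol and SAP*

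**What the plan says.** - **Section 17.1** (repeated in the data analysis text at the end of the document): "Chi-square and Fisher's exact test will be used to compare adverse events (e.g., systemic reaction, anaphylaxis, SOB, dyspnea, excess bleeding or hematoma formation". The same sentence applies these tests to first-attempt success. The section also defines a post-procedure period of 2 minutes after needle withdrawal.
- **Section 19.1**: "This is an observational study, involves minimum risk to participant". It anticipates no safety issue. The prompts "19.3 Describe any safety endpoints" and "19.4 Describe how the safety information will be collected" are both answered as not applicable, and so are 19.2 and 19.5 to 19.9.
- **Section 4.1**: "This is a single-center, randomized, open label, placebo controlled clinical trial".
- **Section 10.2**: "We will collect demographic data, reason for venipuncture, PBCL score, facial pain score etc". Adverse events are not named, though the list is open-ended. Section 10.3 lists three instruments: a data collection form, the PBCL and the Faces scale.
- **Section 20.1** withdraws any child whose first venipuncture fails. **Section 20.2** adds: "If a subject is withdrawn from the study, we will not collect any data from the subject".
- **Section 11.2**: participation lasts 5 to 10 minutes, without follow-up.

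**The concern.** A between-arm test of adverse events needs defined events, someone to record them, an observation window, and a count of children observed in each arm. Section 17.1 assumes all of these. Section 19 disclaims the endpoint and the collection, on a description of the study that 4.1 contradicts.

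The withdrawal rule is a separate problem. Whether the first stick fails is known only after the child has been randomised and has received the assigned intervention. Dropping these children therefore happens after randomisation and could differ by arm. Any bleeding or hematoma in a failed attempt would not be counted. The encounter is short and has no follow-up, so events not recorded at the bedside may be hard to recover. At stake is whether a statement about adverse events by arm would describe all treated children or only those whose first stick succeeded.

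**Working it through.** **1. Setting the sections side by side**

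| What the 17.1 comparison needs | What the rest of the plan provides |
|---|---|
| Events as endpoints | 19.3: not applicable. Examples appear only in 17.1, without definitions. |
| A means of collection | 19.4: not applicable. 10.2 does not name adverse events. The form is not among the documents. |
| A time and frequency of recording | 19.5: not applicable. |
| A test | 17.1 names two. 19.8: not applicable, a conflict if that item covers the final analysis. |
| All randomised, treated children | 20.1 and 20.2 remove failed first sticks. |
| First-attempt success by arm (same sentence of 17.1) | Needs failures counted by arm, which 20.2 as worded rules out. |

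The video does not fill the gap. Under 10.1, taping stops when the venipuncture is completed, before the 2-minute post-procedure period ends.

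**2. The plan's own figure**

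The only power statement (17.2) is for a chi-square test with w = 0.3, alpha 0.05, 8 degrees of freedom and 80% power. With noncentrality N × w², the required N is 166.9, so 167, or 168 in three equal arms. At N = 168, N × w² = 168 × 0.09 = 15.12 and power is 80.3%. The figure of 168 reproduces. It is not specific to adverse events, and nothing below changes it.

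**3. What zero events would show**

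The exact one-sided 95% upper bound after zero events in n children is 1 − 0.05^(1/n).

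- Complete collection, n = 56 per arm (section 5.1): 1 − 0.05^(1/56) = 0.052, or 5.2%.
- Failed sticks deleted and not replaced. The documents give no failure rate, so these rates are assumptions:
  - 10%: 56 × 0.9 = 50.4, n = 50, bound 5.8%
  - 20%: 56 × 0.8 = 44.8, n = 45, bound 6.4%
  - 30%: 56 × 0.7 = 39.2, n = 39, bound 7.4%

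The numerical loss is modest. The larger change is in meaning: the second set of bounds applies to successful sticks only. If events were not systematically looked for, no bound applies.

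**4. What the comparison can show even when complete**

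The documents give no event rates, so these are assumed.

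- Chance of at least one event in an arm of 56, 1 − (1 − p)^56: 24% at p = 0.5%, 43% at 1%, 68% at 2%, 94% at 5%.
- Pairwise power, two-sided 0.05, normal approximation: Φ{[|p1 − p2|√n − 1.96√(2p̄(1 − p̄))] / √(p1(1 − p1) + p2(1 − p2))}, where p̄ is the mean of p1 and p2.
  - 2% against 10%: (0.5987 − 0.6583) / 0.3311 = −0.18, power 43%.
  - 5% against 10%: (0.3742 − 0.7301) / 0.3708 = −0.96, power 17%.

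For uncommon events the comparison is largely descriptive, and its value rests on complete recording.

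**The case against.** The strongest reply is that the data collection form was submitted separately. Section 10.2 is plainly not exhaustive: first-attempt success is also analysed in 17.1 and also absent from 10.2. Section 10.4 names the electronic chart as a source. Adverse-event fields may exist. This stands. A reader might infer that the comparison cannot be done, that it has no denominator, or that a report of no events would merely reflect non-collection. The documents do not establish any of these; they show only that no section provides for collection and that 19.4 disclaims it.

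Secondly, section 19 is headed as monitoring for subject safety. Items 19.2, 19.6 and 19.7 concern ongoing or cumulative review, and 19.8 can be read the same way. A final comparison is compatible with no interim monitoring. This also stands, so it would be too strong to say that all of section 19 contradicts 17.1. The clear conflict is with 19.3 and 19.4, which ask directly about endpoints and collection.

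Thirdly, the failed-stick rule is itself contradicted by the first-attempt-success comparison, so failures may in practice be counted. That is possible, but it is a second conflict to resolve and does not answer the first. Counting a failure also does not record its adverse events.

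Lastly, adverse events are outside the objectives and the primary outcome, and the protocol describes both active products as FDA approved and in routine use in this department. This bears on severity, not on whether the text conflicts.

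**Conclusion.** The concern holds as an internal inconsistency that should be fixed. It does not undermine the trial's main comparison. Two parts rest on the text alone: 17.1 conflicts with 19.3 and 19.4 (and with 19.8 on one reading), under a description of the study that 4.1 contradicts; and 20.1 and 20.2, followed as written, restrict the adverse-event comparison to successful first sticks and conflict with the first-attempt-success analysis. The second part does not depend on what the form contains.

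The only size that needs no assumed rate is the 5.2% upper bound for zero events in 56 completely observed children. The 5.8% to 7.4% range rests on assumed failure rates of 10% to 30% without replacement. A reader might also infer that failed sticks are where bleeding is most likely. The documents give nothing on this, and the conclusion does not need it. No efficacy result or sample size changes.

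**What to change.** Reconcile 17.1, 10.2, 19 and 20:

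- **10.2 and the data form**: record the events named in 17.1 yes/no for every randomised child, including those with a failed first attempt, through the end of the 2-minute post-procedure period that 17.1 already defines.
- **20.2**: state that these safety data and the first-attempt outcome are kept when a child is withdrawn for a failed stick. The restriction of pain scores to first attempts need not change. Section 20.3 should say whether events already recorded are kept when a family withdraws.
- **19.3, 19.4, 19.5 and 19.8**: answer in line with 17.1. If no interim review is intended, say so in 19.2, 19.6 and 19.7.
- **19.1**: delete the word observational.

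If adverse events will not be collected, remove the comparison from 17.1 and make no safety claim.

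The cost is protocol wording and a few tick-boxes per child, unless the form already has them. A research assistant is already present to film. The downside is that the comparison stays largely descriptive for uncommon events, and the report should say so.
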